## SAP Revision History

Version #	Version date	Reason for Revision
Version 1	Started Nov 2019 – Issued Dec 2020	Objective of SAP: To describe planned analysis of study objectives prior to data analysis (anticipated initial data analysis to be performed December 2021).
Version 2	July 2021	Finalize SAP for submission to FDA: update personnel list, update study design to indicate parallel group design, more detailed description of statistical analysis added.

## 1 BACKGROUND AND STUDY DESCRIPTION

### 1.1 Objective

[figure not shown]
The primary aim of the study is to determine the efficacy of multiple intrathecal (IT) administrations of autologous bone marrow mesenchymal stem cell-derived neural progenitors (MSC-NP) compared to placebo through assessment of disability outcomes in patients with progressive multiple sclerosis (MS). The secondary aim is to determine continued safety and tolerability of multiple IT injections of MSC-NPs in patients with progressive MS.

### 1.2 Study Design

The study is a Phase II, double-blind, placebo-controlled, randomized, parallel group design with a compassionate crossover element. The IT-MSC-NP treatments and all clinical assessments take place at a single center (Tisch MSRCNY). Both the patient and the examining neurologist are blinded to the treatment. The treating clinician ([name], principal investigator) and the cell manufacturing coordinator ([name], co-PI) are not blinded. The total study duration is 3 years upon enrollment. Each subject will initially attend 1 screening visit, 1 visit for bone marrow extraction, and 1 baseline visit. In the first year, each subject will receive 6 intrathecal injections of MSC-NPs or placebo spaced 2 months apart, followed by an outcome assessment visit 3 months after the 6th treatment. In the second year, subjects will cross-over into the opposite group, and will receive 6 intrathecal injections of placebo or MSC-NPs spaced 2 months apart, followed by an outcome assessment visit 3 months after the 12th treatment. There is an additional follow-up visit at the end of year 3.

**Study Name:** Autologous, Bone Marrow-Derived Mesenchymal Stem Cell-Derived Neural Progenitor Cells, Expanded Ex Vivo; Administered Intrathecally (Phase II Trial)

**Principal Investigator:** [name]

### 1.3 Primary and Secondary Outcomes

#### 1.3.1 Primary Outcome

Primary efficacy outcome will be a composite score based on EDSS (our EDSS assessments will be based only on pyramidal and brainstem FSS, and performed by a blinded examiner), T25FW, and 9HPT (EDSS-Plus). Improvement will be defined by at least one of the following three measures:  $\geq 0.5$  improvement in EDSS (if EDSS at entry is  $\geq 6.0$ ) or  $\geq 1.0$  improvement in EDSS (if EDSS at entry is  $\leq 5.5$ ),  $\geq 20\%$  improvement in T25FW, or  $\geq 20\%$  improvement in 9HPT in either dominant or non-dominant upper limb. Assessments will be made at Baseline (within 4 months of first treatment/placebo), Month 6 (just prior to 4th treatment/placebo), Month 13 (3 months post 6th treatment/placebo), Month 20 (just prior to 10th treatment/placebo), and Month 27 (3 months post 12th treatment/placebo). Long-term follow-up assessment will be conducted at Month 36. The primary outcome will be the comparison of the composite scores at Month 13 (3 months after the 6th treatment/placebo).

#### 1.3.2 Secondary Outcomes

- EDSS (Improvement defined by  $\geq 0.5$  improvement in EDSS if EDSS at entry is  $\geq 6.0$ , or  $\geq 1.0$  improvement in EDSS if EDSS at entry is  $\leq 5.5$ )
- T25FW ( $\geq 20\%$  improvement)
- 9HPT ( $\geq 20\%$  improvement)
- MSFC
- 12-item MS Walking Scale
- Urodynamic Studies

**Study Name:** Autologous, Bone Marrow-Derived Mesenchymal Stem Cell-Derived Neural Progenitor Cells, Expanded Ex Vivo; Administered Intrathecally (Phase II Trial)

**Principal Investigator:** [name]

- Progression on MRI (measured by percent change from baseline in total volume of T2 Lesions and percent change from baseline in total brain volume at month 13, month 27, and month 36)
- Time to Progression (measured at month 13, month 27, and month 36)
- Six Minute Walk Test

## 1.4 Eligibility Criteria

### 1.4.1 Inclusion Criteria

- Diagnosis of MS as defined by the McDonald criteria
- Diagnosis of primary progressive or secondary progressive MS
- Between the ages of 18-65 years
- Significant disability shown by an Expanded Disability Status Score (EDSS)  $\geq 3.0$  and  $\leq 6.5$  that was not acquired within the last 12 months
- Stable disease state as evidenced by a lack of gadolinium-enhancing lesions on an MRI and by a stable MRI disease burden (number of T2 lesions and size of lesions) in the last six months and no significant change in EDSS (1 point or more) in the last 12 months
- Must agree to undergo four MRIs: at the time of enrollment, after year 1, after year 2, and after year 3
- Patients either within the geographical area or who are able to arrange reliable travel during the study period

### 1.4.2 Exclusion Criteria

- EDSS  $> 6.5$
- Duration of disease  $> 20$  years at time of screening (duration of disease will be determined by onset of symptoms when symptom onset is clearly defined. In cases where symptom onset is difficult to determine, duration of disease will be based on date of diagnosis).
- Change of disease modifying agent  $< 12$  months prior to beginning treatment. Additionally, no changes in disease modifying agent will be made during the course of the study.
- Change in MS symptom management treatments, including Ampyra (dalfampridine)  $< 6$  months prior to beginning treatment. Additionally, no changes in MS symptom management treatments will be made during the course of the study, unless there has been clinical improvement, in which case, a patient may discontinue a medication
- Start of any new orthotic device or durable medical equipment  $< 6$  months prior to beginning treatment or during the course of the study (patients may discontinue use of these devices during the course of the study if they show clinical improvement).
- All patients who have ever been on Lemtrada (alemtuzumab)

**Study Name:** Autologous, Bone Marrow-Derived Mesenchymal Stem Cell-Derived Neural Progenitor Cells, Expanded Ex Vivo; Administered Intrathecally (Phase II Trial)

**Principal Investigator:** [name]

- All patients who have had any prior stem cell treatments in the past five years
- All patients who have had any prior HSCT treatments
- Pregnant or nursing mothers or any woman intending to become pregnant in the next three years
- All patients will have screening blood tests done. Only patients whose values are in the normal range as determined by the laboratory norms based on age and sex will be allowed to participate. Exceptions may be made for borderline normal laboratory values manifesting no clinical symptoms at the discretion of the Principal Investigator.
- Use of systemic chemotherapeutic or anti-mitotic medications within three months of study start date due to the possibility of interference with bone marrow procedure
- Any patients with a history of or with active malignancy
- Use of steroids within three months of the study start date, as this would suggest an active disease state
- History of cirrhosis due to increased risk of CNS infection
- Significantly uncontrolled hypertension because of increased risk for stroke or CNS hemorrhage.
- Patients with active thyroid disease resulting in hyperthyroidism or hypothyroidism (Only well controlled patients with labs in the normal range will be included) because of hormone influence on cell growth
- History of central nervous system infection or immunodeficiency syndromes due to increased risk of CNS infection
- Preexisting blood disease (such as bone marrow hypoplasia, leukopenia, thrombocytopenia, or significant anemia) due to invasive nature of bone-marrow aspiration
- Previous or current history of a coagulation disorder
- Any metal in the body, which is contraindicated for MRI studies
- Allergy to any of the antibiotics used in this study, e.g. tobramycin, vancomycin, or gentamicin
- Allergy to, or have had adverse reactions to gadolinium or other contrast agents to be used in the study
- Patients with alcohol or other substance abuse problems that may affect stem cell growth; habitual drug (including marijuana and nicotine) abusers, will be excluded from the study
- Other major disease that, in the opinion of the Principal Investigator, would preclude participation in the study
- Patients with HBV, HCV, syphilis, HIV-1, or HIV-2.
- Any evidence of significant cognitive dysfunction based on a screening history and physical examination because it would preclude giving a truly informed consent
- Patients who are enrolled in another clinical trial for MS treatment or who have received any study drug/biologics within the last 6 months. Additionally, while in

**Study Name:** Autologous, Bone Marrow-Derived Mesenchymal Stem Cell-Derived Neural Progenitor Cells, Expanded Ex Vivo; Administered Intrathecally (Phase II Trial)

**Principal Investigator:** [name]

the trial, patients may not enroll in any other clinical trial for MS or any other condition.

- Patients who are anticipated to have difficulty accessing the intrathecal space related to scoliosis, obesity, or any other relevant factors determined by the PI.

## 1.5 Sample Size and Randomization

A total of 50 study subjects will be enrolled based on power analysis based on 20 participants in each group of the Phase II study. Group sample size of 20 in the treatment group and 20 in the placebo group achieve more than 80% power to detect a difference between the group proportions of 35%, using a two-sided Z-test with pooled variance and using a significance level of 0.05. This calculation assumes that 40% of patients in the treatment group and 5% of patients in the placebo group achieve at least one of the EDSS-Plus components. The prevalence of patients with improved outcome is informed by the results of our Phase I trial, in which 40% of patients experienced a decrease of 0.5 or more on EDSS. A total of 50 patients (25 patients in each group) will initially be enrolled to account for an expected attrition rate of 20%.

Subjects will be stratified according to baseline EDSS score (3.0-4.0, 4.5-5.5, 6.0, and 6.5) and disease subtype (SPMS or PPMS), and block randomized within each stratum. The total number of subjects to be enrolled in each subgroup is shown below. Subjects are stratified and block randomized into placebo or treatment group in order of date of enrollment based on randomization scheme designated by [name]. Study subjects are randomized in an equal fashion to study treatment and placebo at initial randomization.

EDSS	SPMS	PPMS
3.0-4.0	10	4
4.5-5.5	10	2
6.0	10	2
6.5	10	2
Total # of patients:	40	10

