9.3 Effectiveness analysis

All statistical analysis will be performed by [name] and her team. Descriptive statistics will be calculated for patients at baseline for the entire cohort

as well as by treatment status. Treatment and placebo group patients will be compared on continuous and discrete baseline characteristics to assess randomization. The EDSS-Plus scale [6] will be used as our primary endpoint with improvement on one or more of the 3 components (EDSS, T25FW and 9HPT). Improvement is defined as ≥ 1 point decrease from baseline EDSS if EDSS at entry is ≤ 5.5 , and a ≥ 0.5 point decrease from baseline EDSS if EDSS at entry is ≥ 6.0 , $\geq 20\%$ positive change in T25FW, and/or $\geq 20\%$ positive change in 9HPT confirmed. The primary endpoint of improvement on one or more of the 3 EDSS-Plus categories between treatment and placebo groups will be assessed bi-varately using the chi-square or Fisher's exact test, as appropriate, at year 1, 2, and 3 of the study. The three components of the EDSS-Plus composite score will also be assessed individually at all time points. A longitudinal linear mixed-effect model will be used to assess longitudinal change (percentage change in mean time) from baseline to 3 years for T25FW and 9HPT, with random intercepts for patients and taking into account treatment status (treatment vs placebo), progression status (SPMS vs PPMS) and time-progression status interaction. Secondary endpoints including 12-item walking scale and urodynamic studies (binary, $\geq 20\%$ improvement in bladder capacity vs $< 20\%$) will also be analyzed. Linear regression models for continuous outcomes and logistic regression models for discrete outcomes will be used to assess the independent effect of treatment status on secondary outcomes, controlling for co-variates. All analyses will be performed in SAS Version 9.4 (SAS Institute Inc., Cary, NC).

Any deviations from the previously described statistical plan will be described and justified in a protocol amendment and/or in the final report submitted to the IND application.

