### **4 STATISTICAL ANALYSIS OF THE PRIMARY AND SECONDARY STUDY OBJECTIVES**

#### **4.1 Analysis of the Primary Study Objective**

##### Primary Outcome:

The primary analysis will include all subjects meeting inclusion and exclusion criteria and who have completed a year of treatment/placebo and the 3 month post-treatment assessment. EDSS Plus composite score from 3 month post-treatment assessment will be compared to baseline.

Descriptive statistics will be calculated for patients at baseline for the entire cohort as well as by treatment status. Treatment and placebo group patients will be compared on continuous and discrete baseline characteristics to assess randomization.

The EDSS-Plus scale will be used as our primary endpoint with improvement on one or more of the 3 components (EDSS, T25FW and 9HPT). Improvement is defined as  $\geq 1$  point decrease from baseline EDSS if EDSS at entry is  $\leq 5.5$ , and a  $\geq 0.5$  point decrease from baseline EDSS if EDSS at entry is  $\geq 6.0$ ,  $\geq 20\%$  positive change in T25FW, and/or  $\geq 20\%$  positive change in 9HPT confirmed. The primary endpoint of improvement on one or more of the 3 EDSS-Plus categories between treatment and placebo groups will be assessed bi-varately using the chi-square or Fisher's exact test, as appropriate, at year 1, 2, and 3 of the study. Adjusted odds ratio (95%CI) between treatment and placebo groups at each time point will be estimated through mixed effect logistic regression with fixed effect of time, treatment, relevant covariates, and random effect of patients. The three components of the EDSS-Plus composite score will also be assessed individually at all time points. A longitudinal linear mixed-effect model will be used to assess longitudinal change (percentage change in mean time) from baseline to 3 years for T25FW and 9HPT, with random intercepts for patients and taking into account treatment status (treatment vs placebo), disease subtype (SPMS vs PPMS) and time-progression status interaction.

**Study Name:** Autologous, Bone Marrow-Derived Mesenchymal Stem Cell-Derived Neural Progenitor Cells, Expanded Ex Vivo; Administered Intrathecally (Phase II Trial)

**Principal Investigator:** [name]

Under parallel design, we will compare the outcomes of interest between the two study treatments, with outcomes at 1 year as the primary time point, secondary analyses will evaluate outcomes at years 2 and 3.

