For comparisons via association tests, number (%) of events in the two groups and p-values from Chi-squared or Fisher's exact test will be reported. For regressions, odds ratios (95% CI) between the two groups and p-values from the mixed-effect model will be reported.

Appropriate method to deal with missing values will be chosen after exploring the data collected. Based on reason(s) and amount of missingness, deletion and/or imputation might be applied.

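### The power statement is for a pooled Z-test, but the primary test is chi-square or Fisher's exact with no selection rule; on a conventional reading, power at 20 per group is about 76%

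*SAP*

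**What the plan says.** SAP 1.5 states that "Group sample size of 20 in the treatment group and 20 in the placebo group achieve more than 80% power", assuming 40% improved on treatment and 5% on placebo. The test behind the figure is given as "using a two-sided Z-test with pooled variance and using a significance level of 0.05". Protocol 9.2 says the same. Both enrol 25 per group to allow for 20% attrition, so 20 per group is the planned analysable number.

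The analysis sections name something else. SAP 4.1 says the EDSS-Plus comparison "will be assessed bi-varately using the chi-square or" Fisher's exact test, as appropriate. Protocol 9.3 has the same choice: "exact test, as appropriate, at year 1, 2, and 3 of the study". The reporting paragraph of SAP 4.1 keeps both open: "For comparisons via association tests, number (%) of events in the two groups and p-values from Chi-squared or" Fisher's. Neither document says when each test applies, whether the chi-square carries a continuity correction, or what power Fisher's test has.

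SAP 4.1 sets the primary comparison "with outcomes at 1 year as the primary time point" and restricts it to eligible subjects "who have completed a year of treatment/placebo and the 3 month post-treatment assessment".

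**The concern.** The power claim belongs to one of the tests that the plan allows. With 20 per group and few placebo responders, the permitted tests differ materially in power, and the assumed rates put the table where analysts commonly switch to Fisher. Two things are at stake. The planned analysis may have less power than the plan states. And the primary conclusion could depend on a choice that can be made after the data are seen.

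**Working it through.** **Inputs.** From SAP 1.5 and protocol 9.2: n = 20 per group, 40% vs 5%, two-sided 0.05, 25 per group enrolled. Not in the documents: the rule of using Fisher when any expected cell count is below 5, and the way in which 40 completers split between groups.

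**Step 1: the plan's figure.** The squared pooled Z statistic equals the uncorrected Pearson chi-square, so the two tests are the same. Exact power is the sum, over all 21 × 21 outcomes (a, b), of Bin(a; 20, 0.40) × Bin(b; 20, 0.05) wherever p ≤ 0.05. Result: 0.8204, which is more than 80% as stated.

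The textbook normal approximation is Φ[(0.35 − 1.96·SE₀)/SE₁].
- SE₀ = √(2 × 0.225 × 0.775/20) = 0.1321
- SE₁ = √(0.40 × 0.60/20 + 0.05 × 0.95/20) = 0.1199
- (0.35 − 0.2588)/0.1199 = 0.760, and Φ = 0.777

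So the statement holds by exact enumeration but not by this approximation. The documents do not say which was used.

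**Step 2: is Fisher a live option?** The pooled rate is (0.40 + 0.05)/2 = 0.225, so the expected number of improvers is 20 × 0.225 = 4.5 per group. With equal groups, the rule picks Fisher when nine or fewer patients improve in total. The probability of this is 0.59.

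**Step 3: power of each permitted test** (same enumeration, 40% vs 5%).

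| Treatment/placebo analysed | Uncorrected chi-square | Expected-count rule | Fisher always | Uncorrected chi-square and Fisher disagree |
|---|---|---|---|---|
| 20/20 | 82.0% | 76.1% | 71.6% | 10.5% |
| 19/21 | 82.2% | 78.6% | 77.4% | 4.8% |
| 21/19 | 81.0% | 76.9% | 76.8% | 4.2% |
| 18/22 | 82.7% | 73.7% | 73.6% | 9.0% |
| 22/18 | 80.7% | 71.1% | 71.0% | 9.7% |
| 17/23 | 84.0% | 72.3% | 71.9% | 12.1% |
| 23/17 | 77.8% | 70.7% | 70.1% | 7.7% |
| 25/25 | 90.7% | 88.3% | 82.2% | 8.5% |

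The splits 17/23 to 23/17 carry 99% of the probability if 40 completers are drawn at random from 25 + 25. Averaged over such splits, power is 81.7%, 75.7% and 74.1% for the three options. A continuity-corrected chi-square has 68.8% at 20/20 and 79.2% at 25/25.

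**Step 4: where the verdict changes.** At every split in the table, Fisher never rejects when the uncorrected chi-square does not. At 20/20 the disagreement is therefore just the difference in power (82.0 − 71.6, or 10.5 points before rounding). Example: 6/20 vs 1/20 gives chi-square = 40 × (6 × 19 − 14 × 1)²/(20 × 20 × 7 × 33) = 4.33, p = 0.038, against Fisher p = 0.092. Another, close to the planning rates: 8/20 vs 2/20 gives 0.028 against 0.065.

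**Step 5: false positives.** The maximum size of the uncorrected chi-square over all common response rates is 5.3% at 20/20, 5.8% at 17/23 or 23/17, and 6.5% at 25/25. At a common rate of 22.5% it is 5.1% at 20/20 and 5.5% at 25/25. Fisher's maximum is 2.5% at 20/20 and 3.3% at 25/25.

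**The case against.** The power sentence is true of the test that it names, and chi-square or Fisher as appropriate is common shorthand. This stands: a reader might infer that the sample-size calculation is wrong, and the documents do not support that. The gap lies between the power statement and the analysis section.

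A reader might also infer that the trial has 71.6% power. That needs Fisher in every trial at exactly 20/20, which the plan does not say. It is also near the low end for Fisher, which gives 77.4% at 19/21 and 76.8% at 21/19. About 76% is the fairer figure, and it rests on an assumed convention.

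Twenty per group is not certain either. Protocol 5.1.1 and 8.4 replace discontinued subjects, protocol 13.1 does not, and these passages must be reconciled. SAP 3 leaves imputation open. If replacement brings the analysed number to 25 per group, the uncorrected chi-square, the expected-count rule and Fisher all exceed 80%. It would go too far to say that the point then disappears: a corrected chi-square is still at 79.2%, and with 23 per group Fisher is at 79.8%.

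Finally, a reader might see a route to inflated false positives. Choosing between the uncorrected chi-square and Fisher after seeing the data can do no worse than always using the former, whose excess is limited (step 5). The cost is mainly lost power and an unsettled verdict.

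**Conclusion.** The point holds as a mismatch between the power statement and the primary test. At the planned 20 completers per group, the stated power is met only if the uncorrected chi-square is used, and then by exact enumeration. A conventional reading of the plan gives about 76%. Fisher in every trial gives about 70 to 77% across likely splits of 40 completers, and a corrected chi-square gives 68.8% at 20/20. The uncorrected chi-square and Fisher would give different primary verdicts in about 4 to 12% of trials, always with the uncorrected chi-square as the significant one.

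These figures assume the plan's 40% and 5%, about 40 completers and, for the 76%, the expected-count-below-5 rule. The plan should be changed, but the point does not invalidate the design.

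**What to change.** In SAP 4.1 (including its reporting paragraph) and protocol 9.3, name one test for the Month 13 primary comparison and remove *as appropriate* there. There are two sound options:

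- **Two-sided Pearson chi-square without continuity correction**, with Fisher as a sensitivity analysis. This matches the power calculation. Its downside is a size slightly above 5% in some configurations (step 5), and its power still depends on the split (77.8% at 23/17).
- **Fisher, or the expected-count rule**, written out in full. SAP 1.5 and protocol 9.2 should then restate power at 20 per group as about 72% or about 76%.

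Under either option, say in SAP 1.5 how the power was computed.

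The adjusted analysis has a similar gap. SAP 4.1 plans a "mixed effect logistic regression with fixed effect of time, treatment, relevant covariates, and random effect of patients". Replace the unspecified covariates with the randomisation factors, EDSS stratum and MS subtype. SAP 2.1 already lists EDSS score and subtype, but only as baseline data.

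The cost is wording in SAP 1.5 and 4.1 and protocol 9.2 and 9.3. No extra patients or data are needed. The second option means accepting a stated power below 80%.

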## 2 VARIABLES FOR ANALYSIS

### 2.1 Analysis of Baseline Data

- Gender (M/F)
- Age at study (years)
- MS subtype (SPMS/PPMS)
- Disease duration (years)
- EDSS score

**Study Name:** Autologous, Bone Marrow-Derived Mesenchymal Stem Cell-Derived Neural Progenitor Cells, Expanded Ex Vivo; Administered Intrathecally (Phase II Trial)

**Principal Investigator:** [name]

